Exclusion Criteria	
 1. Cysts in which FNA is not indicated based on review by the clinician, including potential concern of blood vessel location relative to the cyst. 2. Requirement for anticoagulation using clopidogril, warfarin, or other long acting antiplatelet agents (with the exception of aspirin) that cannot be safely stopped according to institutional guidelines. 3. Standard contraindications for EUS. 4. Known pancreatic pseudocyst. 5. Pregnancy.
Statistical Methods and Sample Size	
The sample size of this study was computed based on the following assumptions on the primary endpoint, as well as for the secondary endpoint c):
 
Primary endpoint considerations:
 
 • The volume of actual aspirated cyst fluid as a function of estimated maximal volume either in 19 G or 19 G Flex Arm is superior by at least 10% compared to the 22 G Arm, detected with 90% conjunctive power, using multiple comparison Hochberg's step up method. • Requires 50 patients in 19 G Flex Arm, and 25 patients each in 22 G and 19 G Arms. 
Secondary endpoint c) considerations:
 
 • Superiority of EUS-FNA success rate in 19 G Flex Arm by 16% or more compared to both the success rate of the 19 G Arm and the 22 G Arm, detected with 80% conjunctive power, using multiple comparison Hochberg's step up method. • Requires 121 patients in 19 G Flex Arm, and 61 patients each in 22 G and 19G Arm, rounded up

	
The final sample size was considered to be the maximum of required sample sizes of the above stated two endpoints to make sure that the both endpoints are properly powered, namely 250 patients.

--	--

1. Introduction

Endoscopic ultrasound fine needle aspiration (EUS-FNA) has become the reference standard for preoperative diagnosis of pancreatic cystic lesions (PCLs).^{1,2} Limitations of EUS-FNA persist however and include poor cytological yield, modest sensitivity to detection of malignancy of neoplastic cysts, and incomplete aspiration of cyst fluid which limits the ability to perform tumor marker and cytological testing. Additionally, EUS-FNA may increase the risk of infectious complications compared to EUS without FNA. Adverse events may include but are not limited to pancreatitis, infection, and bleeding.^{2,3} Overall, however, EUS-FNA is considered a safe and effective procedure.

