9.1. Study Hypothesis and Sample Size Calculation

Sample size was calculated based on assumptions for the primary endpoint as well as for secondary endpoint c):

9.1.1. *Primary endpoint considerations:*

The study hypothesis states that for either of the 19 G Flex and 19 G Arms, the volume of actual aspirated cyst fluid as a ratio (%) of estimated maximal volume is superior by at least 10% compared to that of the 22 G Arm.

The study investigators provided the following experience-based estimate of the primary endpoint (aspirate volume as % of max volume based on EUS image of the cyst):

Figure 4 – Hypothesis Generating References (Primary Endpoint)

Site Investigator	Mean Volume Ratio (%) for 19G and 19Flex needles	Mean Volume Ratio (%) for 22G needles
Investigator 1	80%	50%
Investigator 2	90%	70%
Investigator 3	90% Unilocular cysts, 50% Multi-locular	80%

	cysts, 80% Blended mean	
Investigator 4	90%	90%
Investigator 5	90%	50%
Investigator 6	85%	65%

From the above table, bootstrap method with 10,000 resamples yielded an estimated mean of 67.44% and standard deviation of 15.29% for 22G, and a mean of 85.9% and standard deviation of 4.67% for 19G/19G Flex.

The assumption was made that the mean of the “control group”, namely the 22G arm, will be 67% with a standard deviation of 15.29%.

Two null hypotheses are made:

- H_{01} : Mean volume ratio of 19 G Flex Arm and 22 G Arm are the same
- H_{02} : Mean volume ratio of 19 G Arm and 22 G Arm are the same

The alternative hypothesis is:

- H_1 : Mean volume ratio of 19 G Flex/19G Arm is superior to 22 G Arm

If 50 patients are enrolled in the 19 G Flex Arm and 25 patients each in the 19 G and 22 G Arm, the study will have 90% conjunctive power to detect the rejection of both null hypotheses to demonstrate superiority of the mean volume ratio of 19 G Flex Arm and 19 G Arm to that of 22 G Arm by 10% or more. Thus, a minimum of 100 patients (50+25+25=100) are required.

9.1.2. Secondary endpoint c) considerations:

The study hypothesis states that the EUS-FNA 19 G Flex needle is superior to the EUS-FNA 22 G standard and 19 G standard needles in the secondary endpoint c) measure, which requires access or adequate aspirate volume for two standard assays expected from successful EUS-FNA procedures in PCL assessment indications.

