12 AUG 2016

FINAL

Boston Scientific

Randomized Evaluation of PCLs Using Three EUS-FNA Needles

90869947 Rev/Ver. AG

Page 41 of 46

Design Parameters:

One-sided Type I Error=0.05

Multiple comparison procedure= Hochberg's step up

Total Sample required=100

Rejection region=Right tail

Treatment parameters:

Arm	Mean volume ratio	Standard Deviation	Sample size per group
22G	67	15.29	25
19G	77	4.67	25
19GFlex	77	4.67	50

Overall:

Global (reject any H_i): 0.912

Conjunctive (reject all H_i): 0.901

Secondary endpoint c) considerations:

It is the desire of this study to demonstrate superiority of the EUS-FNA 19 G Flex needle over two other needles:

- One offering the same needle diameter, but without added needle flexibility, namely the standard 19 G needle
- One offering better needle flexibility via a reduced needle diameter, namely the standard 22 G needle

Superiority by 16% or more is deemed clinically significant. Statistical power of 80% is chosen using the multiple comparison Hochberg's method. Test results are shown below, resulting in the requirement for 121 patients for 19 G Flex arm and 61 patients each for 19 G and 22G arm.

Hypothesis:

$H_i: \pi_i - \pi_0 \leq 0$ Versus $K_i: \pi_i - \pi_0 >$ for $i=1,2$

Design Parameters:

One-sided Type I Error=0.05

Multiple comparison procedure= Hochberg's step up

Total Sample required=243

Rejection region=Right tail

Treatment Parameters:

Arm	Response rate	Sample size per group
19GFlex	0.91	121
19G	0.75	61
22G	0.75	61

Overall:

Global (reject any H_i): 0.947

Conjunctive (reject all H_i): 0.808

C.3 Diagnostic Accuracy Measures

Diagnostic accuracy is defined in terms of “disease state” and the following three disease state categories will be used in this study in order to assess diagnostic accuracy of EUS-FNA:

- “*Disease State per EUS-FNA*”: This measure is derived from the results of the cytology and chemistry assays of the cyst aspirate. Cysts will be classified as *serous cyst*, *mucinous cyst*, *IPMN*, or *pseudocyst* based on the table below.⁴ If any of the aspirate assays are not performed or the results from the two aspirate-based assays do not follow the table below, then the Disease State per EUS-FNA will be classified as *Indeterminate*. The Disease State per EUS-FNA will be recorded on the *Cytology and Chemistry Results CRF*.

Disease State per EUS-FNA	Cytology	Cyst Fluid CEA (ng/mL)
Serous	Bland PAS +*	< 0.5
Mucinous	Mucinous	> 200
IPMN	Mucinous	> 200

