Exclusion Criteria	
 
1. Cysts in which FNA is not indicated based on review by the clinician, including potential concern of blood vessel location relative to the cyst.
 
2. Requirement for anticoagulation using clopidogril, warfarin, or other long acting antiplatelet agents (with the exception of aspirin) that cannot be safely stopped according to institutional guidelines.
 
3. Standard contraindications for EUS.
 
4. Known pancreatic pseudocyst.
 
5. Pregnancy.
 

Statistical Methods and Sample Size	
The sample size of this study was computed based on the following assumptions on the primary endpoint, as well as for the secondary endpoint c):
 
Primary endpoint considerations:
 
 
• The volume of actual aspirated cyst fluid as a function of estimated maximal volume either in 19 G or 19 G Flex Arm is superior by at least 10% compared to the 22 G Arm, detected with 90% conjunctive power, using multiple comparison Hochberg's step up method.
 
• Requires 50 subjects in 19 G Flex Arm, and 25 subjects each in 22 G and 19 G Arms.
 
 
Secondary endpoint c) considerations:
 
 
• Superiority of EUS-FNA success rate in 19 G Flex Arm by 16% or more compared to both the success rate of the 19 G Arm and the 22 G Arm, detected with 80% conjunctive power, using multiple comparison Hochberg's step up method.
 
• Requires 121 subjects in 19 G Flex Arm, and 61 subjects each in 22 G and 19G Arm, rounded up
 
 
The final sample size was considered to be the maximum of required sample sizes of the above stated two endpoints to make sure that the both endpoints are properly powered, namely 250 subjects.

A flow chart illustrating the study design is provided in **Figure 1** below.

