### 3 ENDPOINT ANALYSIS

#### 3.1 Primary Endpoint

##### 3.1.1 Hypotheses

The primary endpoint is “Volume of aspirated cyst fluid as a function of estimated maximal volume based on pre-aspiration EUS measure of cyst diameter (s) (% aspiration of total estimated volume).”

Analysis Approach:

% aspiration of total estimated volume is calculated overall and for each arm (19 G Flex, 22 G, 19 G) and/or a combination of arms such as 19G Flex and 19G, for each and combined morphologic characteristics, and for no salvage subjects. If there is multilocular morphology, the primary endpoint is calculated for measurements of the largest locule.

Valid Data Sources:

- Procedure Form: sections “PCL Characteristics” and “Post-Aspiration Assessment”

Valid Data Points:

- Morphology: Unilocular (Pre-aspiration EUS measures)
  - Maximal diameter (long axis) (mm)
  - Perpendicular measurement (short axis) (mm)
- Morphology: Multilocular (Pre-aspiration EUS measures)
  - Measurements of the largest locule
    - Maximal diameter (long axis) of the largest locule (mm)
    - Perpendicular measurement (short axis) of largest locule (mm)
- Total volume of aspirate (Post-aspiration assessment)

Formula:

$$\% \text{ aspiration of total estimated volume} = \frac{A-B}{A} \times 100 \%$$

Volume is computed using the standard geometric formula  $\left(\frac{4}{3}\pi R^3\right)$  where R is half the long axis. The volume unit is in cc. “A” is calculated by the image during pre-procedure measurements. “B” is calculated by the image during post-procedure measurements.

Hypotheses:

$H_{0i}: \mu_i - \mu_0 \leq 0$  Versus  $H_{1i}: \mu_i - \mu_0 > 0$  for  $i=1, 2$ ;

where  $\mu_0$  is mean volume percentage of 22 G Arm,  
 $\mu_1$  is mean volume percentage of 19 G Flex Arm, and  
 $\mu_2$  is mean volume percentage of 19 G Arm.

Superiority by 10% or more is deemed clinically significant.

The multiple comparison Hochberg's step up method will be used.

The analysis population for the primary endpoint will be the Intent to Treat and Per-protocol analysis sets.

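### The primary-endpoint claim of 90% power with 100 patients uses the spread of six investigators' estimated means as the between-patient SD, so it is unsupported; the enrolled 250 is not shown to be too few

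*Protocol*

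**What the plan says.** Figure 4 in Protocol 9.1.1 lists, for six investigators, an estimated mean percentage aspirated with the 19 G and 19 G Flex needles together and another with the 22 G needle. The text below it says the "bootstrap method with 10,000 resamples yielded an estimated mean of 67.44% and standard deviation of 15.29% for 22G". For the two larger needles taken together, the same step is reported to give "a mean of 85.9% and standard deviation of 4.67% for 19G/19G Flex". One investigator's entry for the 19 G needles is split by cyst type: "90% Unilocular cysts, 50% Multi-locular" cysts, with a blended mean of 80%.

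Appendix C.2 and SAP 3.1.2 tabulate these SDs by arm beside the number of patients per arm: 22 G mean 67, SD 15.29, n = 25; 19 G mean 77, SD 4.67, n = 25; 19 G Flex mean 77, SD 4.67, n = 50. With one-sided 5% and Hochberg's procedure, the stated power is 0.901 conjunctive and 0.912 global.

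The resulting requirement appears in five places:

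- Protocol synopsis: "Requires 50 patients in 19 G Flex Arm, and 25 patients each in 22 G and 19 G Arms"
- Protocol 9.1.1: "Thus, a minimum of 100 patients (50+25+25=100) are required"
- Appendix C.2: "Total Sample required=100"
- SAP section 1: "Requires 50 subjects in 19 G Flex Arm, and 25 subjects each in 22 G and 19 G Arms"
- SAP 3.1.2, as a total of 100 subjects

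The final 250 is the larger of the requirements for the primary endpoint (100) and secondary endpoint c (243), raised to 250 for attrition. Both summaries say this makes sure that both endpoints are properly powered.

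**The concern.** A power calculation for a difference in arm means needs the SD between patients within an arm. Six investigators' views of what the mean is can agree closely while patients vary widely, or the reverse. Their spread is not an estimate of the quantity the formula needs.

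Two features of the plan's own figures also sit badly with the inputs. The assumed 22 G variance is more than ten times the 19 G variance, although all arms draw on one randomised population. And the one investigator who separated cyst types gave values 40 points apart for the 19 G needles, which is hard to square with a patient SD of 4.67.

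At stake is the only justification given for the primary-endpoint power. The final sample size came from another endpoint, so the question is what power the primary comparison has at the size enrolled and in smaller sets. SAP 3.1.1 also calculates the endpoint "and for no salvage subjects" and in the per-protocol set, and SAP 5.4 repeats it without outlying sites. A reader who takes 100 patients as enough would judge those sets too favourably.

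**Working it through.** **1. Reproducing the stated power.** Inputs from Appendix C.2: difference 77 − 67 = 10; SD 15.29 (22 G) and 4.67 (both 19 G arms); n = 25/25/50; one-sided α = 0.05. Under Hochberg, both hypotheses are rejected when the larger p-value is at most 0.05.

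Pairwise normal approximation, Φ(10/SE − 1.645):

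- 19 G v 22 G: SE = √(15.29²/25 + 4.67²/25) = 3.20, power 0.931
- Flex v 22 G: SE = √(15.29²/25 + 4.67²/50) = 3.13, power 0.940

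Simulating the three arms with the shared 22 G control and Welch t gives 0.904 conjunctive and 0.915 global, against 0.901 and 0.912. With the SAP's normal reference the figures are 0.91 and 0.93. The arithmetic is sound.

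**2. Where the SDs come from.** From the six values in Figure 4:

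- 22 G (50, 70, 80, 90, 50, 65): mean 67.5; SD 14.65 (divisor 6) or 16.05 (divisor 5)
- 19 G (80, 90, 80, 90, 90, 85): mean 85.83; SD 4.49 or 4.92

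The stated 15.29 and 4.67 lie inside these ranges, so they are the spread of the investigators' means. They are not bootstrap standard errors of the mean, which would be about 14.65/√6 = 6.0 and 4.49/√6 = 1.8. The implied variance ratio is (15.29/4.67)² = 10.7.

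**3. A figure implied by the plan's own table.** If the 80% blended mean is a case-mix average of 90% and 50%, the unilocular share is (80 − 50)/(90 − 50) = 0.75. The mix alone then gives an SD of 40 × √(0.75 × 0.25) = 17.3. This is one investigator's implied value under that reading, not a proven floor.

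**4. Conjunctive power for a 10-point difference** (Welch t, Hochberg):

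| SD 22 G / 19 G arms | 25/25/50 | 61/61/121 | Total for 90% at 2:1:1 |
|---|---|---|---|
| 15.29 / 4.67 (as stated) | 0.90 | 0.999 | 100 (as stated) |
| 15.29 / 15.29 | 0.67 | 0.97 | 4 × 44 = 176 |
| 15.29 / 17.3 | 0.61 | 0.95 | 4 × 50 = 200 |
| 17.3 / 17.3 | 0.56 | 0.92 | 4 × 56 = 224 |

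Columns are in the order 22 G / 19 G / Flex. The SAP's normal reference raises the 25/25/50 results in the last three rows to 0.69, 0.63 and 0.57, and changes the larger-sample results in those rows by at most 0.005.

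**5. Larger common SDs at 121/61/61** (assumptions; the documents give none): 0.90 at SD 18, 0.83 at 20, 0.64 at 25 and 0.48 at 30. Power is 0.90 at SD 18.1 and 0.80 at SD 20.9.

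**6. If the true gap were that of Figure 4.** The bootstrap means differ by 85.9 − 67.44 = 18.46 points. With a gap of about 18.4, power at 121/61/61 is 0.99 at SD 25 and 0.95 at SD 30. At 25/25/50 it is 0.99, 0.99 and 0.98 under the last three rows of the table.

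**7. A separate, minor mismatch for endpoint c.** Protocol 9.1.2 reports the meta-analysis as 75% with interval 67–90%. Appendix C.1 gives 73.9% (71.1–76.7) for the fixed-effect model and 80.4% (67.5–90.7) for the random-effects model. The text pairs roughly the random-effects interval with a point estimate that neither model gives.

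Exact binomial enumeration with the SAP's pooled z at 121/61/61 gives 0.804 conjunctive and 0.947 global for 91% v 75%, against the stated 0.808 and 0.947. Keeping the 16-point gap, conjunctive power is 0.78 at a control rate of 73.9% and 0.93 at 80.4%. With Flex held at 91% and control at 80.4%, it is 0.48.

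**The case against.** The strongest reply is that the 100 decides nothing. Enrolment follows endpoint c, and 121/61/61 exceeds 90% under all three alternative SD sets in the table. The 10-point target is also well below the gap in Figure 4; if that gap were true, even 100 patients would give 0.98 or more under those SDs. Both points stand, and they are why no change to enrolment is asked for. They do not rescue the claim, because the plan names 10 points as the clinically significant difference and attaches 90% power to that.

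Next, the alternative SDs are not measurements. The value 15.29 has the same faulty origin, 17.3 rests on one investigator's entry with no variation within cyst type, and applying 17.3 to 22 G goes beyond what that entry covers. This is fair: 176 to 224 is illustrative. It shows how strongly the requirement depends on the SD, not what the SD is.

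Randomisation equalises baseline characteristics, not outcome variance under different needles. A narrower needle could give more variable results, and the SAP statistic allows unequal variances. So the ratio of 10.7 is implausible rather than impossible.

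The protocol is open that the values are experience-based, and nothing in either document tells anyone to compare a subset with 100. The harm in subsets is therefore a risk of misreading, not a planned step.

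Finally, the meta-analysis point concerns another endpoint, 9.1.2 already calls 75% an assumption, and the 0.48 case abandons the 16-point gap. It is kept here only as a small reporting correction.

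**Conclusion.** The concern holds. The primary-endpoint power statement is computed correctly from the wrong quantity: a spread between investigators stands in for a spread between patients, and no patient-level SD is available to replace it. The 0.901/0.912 figures and the 100-patient requirement are therefore unsupported. With SDs built from the plan's own numbers, conjunctive power at 100 patients is 0.56 to 0.67 rather than 0.90.

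The trial is not shown to be underpowered, and it is not shown to be adequately powered either. At 121/61/61 and a 10-point difference, 90% holds up to a common SD of about 18 and 80% up to about 21; power is 0.64 at SD 25 and 0.48 at SD 30. The assurance in both summaries that the primary endpoint is properly powered is conditional on an SD nobody has stated.

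These results assume normal data and, apart from the second alternative in the table, equal SDs across arms. SDs above 17.3 are assumptions. This should be corrected because it misstates the basis of the primary analysis, but it does not threaten the design.

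**What to change.** In the synopsis, Protocol 9.1.1, Appendix C.2, SAP 1 and SAP 3.1.2, withdraw the 100-patient requirement and the 0.901/0.912 figures. Describe 15.29 and 4.67 as spread between investigators. Replacement text could read:

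> The patient-level SD is not known. With 121/61/61 patients and a 10-point difference, conjunctive power is 0.97, 0.90, 0.83, 0.64 and 0.48 for a common SD of 15.29, 18, 20, 25 and 30. Power of 90% holds up to an SD of about 18, and 80% up to about 21.

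In Protocol 9.1.2, report one meta-analysis model with its own interval, keep 75% as a planning assumption rather than the result of the meta-analysis, and show endpoint c power for control rates from 74% to 80%, saying whether the 16-point gap or the 91% Flex rate is held fixed.

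The cost is wording in the protocol and SAP. Enrolment need not change. The stated power becomes less favourable and openly depends on an SD the plan has not measured.

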9.2. Enrollment per Investigational Site

A total of 250 patients will be enrolled in this trial at 7 to 12 investigational sites. To avoid that enrollment be too heavily biased towards one site, an enrollment maximum by site will be instituted per clinical study agreement between each investigational site and the Sponsor.

Enrollment controls are discussed in **Appendix B.13**.

9.3. Data Analysis

The Intent-to-treat (ITT) cohort will consist of all randomized patients, namely patients who signed the ICF, met all eligibility criteria (see note below), were randomized to one of three study arms, and experienced echoendoscope insertion and attempted EUS-FNA procedure. Subjects in this cohort, independent of whether EUS-FNA was successful or not, will be counted towards the enrollment ceiling. Any adverse events occurring or resulting from a treatment attempt will be collected.

NOTE:

12 AUG 2016

FINAL

Boston Scientific
 Randomized Evaluation of PCLs Using Three EUS-FNA Needles
 90869947 Rev/Ver. AG
 Page 25 of 46

Exclusion criteria #1 may be documented after a patient was randomized and the EUS procedure was started. In such cases, the patient will be excluded from the study and no longer be a part of the ITT cohort.

The Modified Intent-to-treat population will consist of ITT population with salvage, namely the patients with 19G + Salvage, 22G + Salvage, and 19G Flex+ Salvage.

The per-protocol (PP) cohort will consist of the subset of the ITT patients in whom the target lesion could be reached and EUS-FNA yielded any aspirate, used the assigned needle, and there were no major protocol deviations. All endpoints will be analyzed for the ITT and PP study populations, for all patients and stratified by EUS-FNA needle type (by randomization arm).

Justification for pooling of data from all study sites will be assessed using standard poolability tests.

Multivariate analyses will be carried out to assess potential correlations between the primary endpoint and PCL location, PCL size, route of access (duodenal, esophageal, or gastric), needle used, and number of locules.

The following analyses are planned:

- Informal interim analysis after study completion of approximately 30 subjects (Phase I) to assure that the data structure is robust for data analyses; no decisions pertaining to enrollment will be made based on findings of this interim analysis.
- Informal interim analysis after study completion of approximately 100 subjects (30 Phase I + 70 Phase II) to finalize endpoint programs and validate them for end of study data analysis; no decisions pertaining to enrollment will be made based on findings of this interim analysis.
- Formal final analysis after study completion of all subjects (30 Phase I + 220 Phase II).

A statistical analysis plan will be in place prior to enrollment. Changes to the plan or additional analyses conducted will be identified as *ad hoc* analyses.

All statistical analyses will be done using The SAS System software, version 8 or higher (Copyright © 2000 SAS Institute Inc., [name], USA. All rights reserved). Subject demographics, medical history, risk factors, pre- and post-procedure characteristics, and outcome variables will be summarized using descriptive statistics for continuous variables (mean, standard deviation, number of observations, minimum and maximum) and frequency statistics (percent of conformers, number of conformers, number of observations) for discrete variables.

10. Potential Risks

